## 7.1.1 DOCUMENTATION OF ADVERSE EVENTS

Safety data will be recorded on a specifically designed case report form (CRF). All serious adverse events (SAEs) or reactions (SARs) will be reported on a SAE report form in addition to CRFs. Throughout the study, the investigator will record all adverse events on the appropriate CRF regardless of their severity or relation to study medication or study procedure. The investigator will treat participants experiencing adverse events appropriately and observe them at suitable intervals until their symptoms resolve or their status stabilizes.

SAEs will be reported within 24 hours of the Site Study Team becoming aware of the event. All SUSARs will be reported by the CI to the relevant Competent Authority and to the REC and other parties as applicable. For fatal and life-threatening SUSARs, this will be done no later than 7 calendar days after the Sponsor or delegate is first aware of the reaction. Any additional relevant information will be reported within 8 calendar days of the initial report. All other SUSARs will be reported within 15 calendar days. All SAE information must be recorded on an SAE form and faxed, or scanned and emailed, to the JRCO ([contact] or via email to [contact]).

Both SAEs and SARs will be reported to the Independent Data Monitoring Committee (IDMC). The IDMC has the authority to recommend termination of the trial because of safety findings. SARs will also be reported to MHRA through the yellow card system.

## 7.2 GRADING AND ATTRIBUTION OF ADVERSE EVENTS

### 7.2.1 NON-ALLERGIC REACTIONS

The study site will grade the severity of adverse events experienced by study participants according to the criteria set forth in the NCI-CTCAE Version 3.0 ([http://ctep.cancer.gov/protocolDevelopment/electronic\\_applications/docs/ctcae3.pdf](http://ctep.cancer.gov/protocolDevelopment/electronic_applications/docs/ctcae3.pdf)).

This document provides a common language to describe levels of severity, to analyse and interpret data, and to articulate the clinical significance of all adverse events.

Adverse events will be graded on a scale from 1 to 5 according to the following standards in the NCI-CTCAE manual:

- Grade 1 = mild adverse event.
- Grade 2 = moderate adverse event.
- Grade 3 = severe and undesirable adverse event.
- Grade 4 = life-threatening or disabling adverse event.
- Grade 5 = death.

All adverse events will be recorded and graded whether they are or are not related to disease progression or treatment. The NCI-CTCAE grades will be the primary source for scoring.

The relation, or attribution, of an adverse event to study participation will be determined by the investigator and recorded on CRF and/or SAE reporting form. The assignment of the causality should be made by the investigator responsible for the care of the participant using the definitions below (Table 2). If any doubt about the causality exists the local investigator should inform the study coordination centre who will notify the Chief Investigators. The pharmaceutical companies and/or other clinicians may be asked to advise in some cases.

In the case of discrepant views on causality between the investigator and others, all parties will discuss the case. In the event that no agreement is made relating to a SUSAR, the MHRA will be informed of both points of view.

**Table 2: Assignment of causality for adverse events**

Relationship	Description
Unrelated	There is no evidence of any causal relationship
Unlikely	There is little evidence to suggest there is a causal relationship (e.g. the event did not occur within a reasonable time after administration of the trial medication). There is another reasonable explanation for the event (e.g. the participant’s clinical condition, other concomitant treatment).
Possible	There is some evidence to suggest a causal relationship (e.g. because the event occurs within a reasonable time after administration of the trial medication). However, the influence of other factors may have contributed to the event (e.g. the participant’s clinical condition, other concomitant treatments).
Probable	There is evidence to suggest a causal relationship and the influence of other factors is unlikely.
Definitely	There is clear evidence to suggest a causal relationship and other possible contributing factors can be ruled out.
Not assessable	There is insufficient or incomplete evidence to make a clinical judgement of the causal relationship.

**7.2.2 GRADING AND ATTRIBUTION OF ADVERSE EVENTS: ALLERGIC REACTION**

Allergic reactions to LAIV will be determined using the World Allergy Organisation (WAO) criteria for allergic reactions to immunotherapy (Table 3). **For the purpose of this study**, mild symptoms of an allergic reaction (ie. non-anaphylactic symptoms) will be classified as non-serious adverse event, and should be documented on the CRF.

**Anaphylaxis** will be defined as per the case definition and guidelines as described by the Brighton Collaboration Anaphylaxis Working Group (see appendix 4).

**Any symptoms requiring treatment for anaphylaxis** (adrenaline, steroids, salbutamol) **will be classified as a SERIOUS ADVERSE REACTION** and will be documented on both the CRF and a SAE form. The local investigator should also make a notification to the MHRA through the MHRA yellow card scheme.

Grade 1	Grade 2	Grade 3	Grade 4	Grade 5

Symptom(s)/sign(s) of 1 organ system present*
 
Cutaneous Generalized pruritus, urticaria, flushing, or sensation of heat or warmth†
 
or
 
Angioedema (not laryngeal, tongue or uvular)
 
or
 
Upper respiratory Rhinitis - (eg, sneezing, rhinorrhea, nasal pruritus and/or nasal congestion)
 
or
 
Throat-clearing (itchy throat)
 
or
 
Cough perceived to originate in the upper airway, not the lung, larynx, or trachea
 
or
 
Conjunctival Erythema, pruritus or tearing
 
Other Nausea, metallic taste, or headache
	
Symptom(s)/sign(s) of more than 1 organ system present
 
or
 
Lower respiratory Asthma: cough, wheezing, shortness of breath (eg, less than 40% PEF or FEV1 drop, responding to an inhaled bronchodilator)
 
or
 
Gastrointestinal Abdominal cramps, vomiting, or diarrhea
 
or
 
Other Uterine cramps
	
Lower respiratory Asthma (eg, 40% PEF or FEV1 drop NOT responding to an inhaled bronchodilator)
 
or
 
Upper respiratory Laryngeal, uvula, or tongue edema with or without stridor
	
Lower or upper respiratory Respiratory failure with or without loss of consciousness
 
or
 
Cardiovascular Hypotension with or without loss of consciousness
	Death

**Table 3:** World Allergy Organisation (WAO) Grading System for allergic reactions to immunotherapy

## 7.3 REPORTING PROCEDURES

All adverse events should be reported. Depending on the nature of the event the reporting procedures below should be followed. Any questions concerning adverse event reporting should be directed to the study coordination centre in the first instance. A flowchart is provided overleaf to aid the reporting procedure.

### 7.3.1 NON SERIOUS AR/AES

[figure not shown]
All such events, whether expected or not, should be recorded in the adverse event section of the relevant case report form and reported to the study CI within one month of the form being due.

### 7.3.2 SERIOUS AR/AES

Fatal or life threatening SAEs and SUSARs should be reported on the same day as the site is made aware of the event. The SAE form asks for nature of event, date of onset, severity, corrective therapies given, outcome and causality (i.e. unrelated, unlikely, possible, probably, definitely). The responsible investigator should determine the causality of the event. Additional information should be sent to the CI within 5 days if the reaction has not resolved at the time of reporting. Any expected SAR will also be reported via the MHRA yellow card system.

**SAEs:** An SAE form should be completed and emailed to the study CI immediately, who will in turn inform the JRCO ([contact] or via email to [[contact]](mailto:[contact])) within 24 hours.

**SUSARs:** All SUSARs will be reported by the CI to the relevant Competent Authority (MHRA) and to the REC and other parties as applicable. For fatal and life-threatening SUSARs, this will be done no later than 7 calendar days after the Sponsor or delegate is first aware of the reaction. Any additional relevant information will be reported within 8 calendar days of the initial report. All other SUSARs will be reported within 15 calendar days.

Contact details for reporting SAEs and SUSARs:		
Study CI:	[contact]	Email: [contact]
Compliance Office:	[contact]	Email: [contact]

## 8. ASSESSMENT AND FOLLOW-UP

### 8.1 CLINICAL ASSESSMENTS

#### 8.1.1 ALLERGY TESTING

No allergy testing will be performed as part of this protocol.

#### 8.1.2 LUNG FUNCTION TESTING

Where study participants are able to comply, lung function will be performed prior to LAIV using the system in use at each centre and according to local protocol. Data relating to bronchodilator responsiveness (BDR) will be collected if performed for routine clinical assessment. For children with non-severe symptoms, an assessment of peak flow using a peak flow meter will suffice, although formal lung function is preferable.

#### 8.1.2 CLINICAL OBSERVATION / MONITORING OF PATIENTS BY CLINICAL STAFF

Patients will have baseline observations (temperature, heart rate, respiratory rate, oxygen saturations, lung function (FEV1 and/or PEFR)) performed prior to LAIV administration, with clinical respiratory and dermatological assessment at the same time.

Children will be observed for at least 20 minutes after LAIV in a safe environment with appropriate clinical supervision and access to paediatric resuscitation facilities and trained staff, in the event of a severe allergic reaction.

#### 8.1.3 ASTHMA CONTROL ASSESSMENT PRE AND 4 WEEKS POST VACCINATION

Participants' families will be asked to complete a questionnaire to determine their child's asthma symptoms and control, using a validated tool at visit 1:

- In children age 2-4 years: TRACK questionnaire (Appendix 1)
- In children age 5-11 years: C-ACT questionnaire (Appendix 2a)
- In children age 12+ years: ACT questionnaire (Appendix 2b)

As part of the CRF, the questions on the Asthma Control Questionnaire (ACQ, Appendix 3) will also be completed. While the (C-)ACT and TRACK questionnaires assess asthma symptoms over the preceding 4 weeks, the ACQ assesses symptoms and control over the preceding 7 days and also includes lung function; the ACQ may therefore be more representative of asthma control at the time of vaccination. The (C-)ACT will be completed first, before the ACQ.

Families will be asked to complete a further questionnaire 4 weeks after vaccination. In general, this will be done using an online questionnaire. Families will be asked at their first

visit as to whether they prefer to be contacted by telephone by the study team, or receive an email request with a link to a secure, online survey. Either way, the survey will take 2-3 minutes to complete. A guide for the telephone call is provided in Appendix 6. These data will be recorded on a CRF.

If the family fails to respond to the email request, the local study team will attempt to contact the family by telephone. If, after three attempts (on three separate days), the local study team is unable to contact the family, the child will be deemed lost to follow up and this will be documented on the CRF, which will then be closed.

At the Royal Brompton, participants will be invited to return to hospital for the 4 week follow-up (which will, in general, coincide with a routine clinic follow-up appointment). The follow-up questionnaires will be completed at this visit, along with some further repeat assessments (section 8.3).

## 8.2 TELEPHONE FOLLOW UP

Participants' families will be contacted by the local research team at least 72 hours after LAIV administration (and within 7 days, to allow for weekends), to determine whether their child has experienced any delayed symptoms which might be attributable to the vaccine. This telephone consultation will take approximately 2 minutes. A guide for this telephone call is provided in Appendix 5. These data will be recorded on the CRF. Following this, the CRF will be deemed complete and forwarded to the coordinating centre.

If after three attempts (on three separate days) the local study team is unable to contact the family, the child will be deemed lost to follow up and this will be documented on the CRF, which will then be closed.

## 8.3 ADDITIONAL CLINICAL ASSESSMENTS (ROYAL BROMPTON SITE ONLY)

Participants at the Royal Brompton Hospital site will undergo further clinical assessments, immediately prior to and 4 weeks after LAIV. Thus, participants at the Royal Brompton will be asked to return 4 weeks later for these repeat assessments. Data will be collected on a supplementary clinical record form.

The planned additional assessments are as follows:

### 1. Measurement of fractional exhaled nitric oxide (FeNO)

Exhaled nitric oxide is a marker thought to represent inflammation in the airways. This non-invasive technique is approved by NICE for the diagnosis and monitoring of asthma in both children and adults. For most children at this site, FeNO is measured as part of routine clinical care. For school-aged children, exhaled nitric oxide will be measured according to local protocol. For preschool children, exhaled breath will be collected during normal tidal breathing into a bag and nitric oxide measured in the collected gas ("offline" method). This technique has been established as a routine test at the Royal Brompton Hospital.

 Measuring fractional exhaled nitric oxide concentration in asthma: NIOX MINO, NIOX VERO and NObreath NICE diagnostics guidance [DG12] Published date: April 2014.

## 2. Induced Sputum

This is also a routine clinical test in the severe asthma clinic. Hypertonic saline will be given via a nebuliser and the child asked to cough any phlegm into a universal container. In preschool children, the sputum sample can be obtained using a combination of chest physiotherapy and suction. The procedure will only be undertaken where children are clinical well (and thus eligible for LAIV). The sample will be assessed in the laboratory for inflammatory cells and any excess stored at -80°C for analysis of inflammatory cytokines. Where consent is provided, any residual sample will be stored for future research.

## 3. Paediatric Asthma Quality of Life Questionnaire (PAQLQ)

Children aged 7+ years and their caregiver will be asked to complete the PAQLQ, a validated assessment of health-related quality of life in asthma.

## 8.4 NASAL SWABBING AND SAMPLE MANAGEMENT

### 8.4.1 COLLECTION OF NASAL SWAB

Parents will be asked to collect up to 3 nasal swabs in the week following LAIV administration. This will involve putting a swab, which looks like a large cotton bud, into the nostril and moving it around for up to a minute.

### 8.4.2 LABELLING, DESPATCH, AND STORAGE OF SAMPLES

Each participant will be assigned a unique identifying number during the enrolment process, according to the Standard Operating Protocol in respect of participant identification for the study. The participant number will be linked to a pre-generated sample barcode for every clinical sample taken, which can be scanned at the testing laboratory.

Samples will be sent to the receiving laboratory at the Virus Reference Division, PHE Colindale by Royal Mail using approved packaging which will be supplied to each family. A brief paper form will be completed by parents to confirm date of sampling. All samples will be logged locally, to enable the identification of any lost or delayed samples and provide a log of where samples are currently stored.

Samples arriving at the receiving laboratory at the Virus Reference Division, PHE Colindale without accompanying paperwork will be initially processed (given that consent has already been obtained) but any results embargoed until confirmatory paperwork has been received from the family.

Samples will be initially processed from the administrative perspective and stored until formal processing in batches. Not all swabs received will undergo viral detection and quantification: swabs will be selected from representative cohorts of individuals, by previous

influenza vaccination status: no previous vaccination, previous LAIV only, previous injected influenza vaccine only. This will allow an assessment of the impact of previous LAIV receipt on viral shedding, something necessary to determine the effect of prior influenza immunisation on viral shedding. Any swabs not included in the viral quantification will be handled as per section 8.4.3.

#### 8.4.3 HANDLING OF RESIDUAL SAMPLES ON COMPLETION OF TESTING

During the consent process, parents/guardians will be asked for consent to keep their child's residual samples (if any) to be used for further research to improve understanding of vaccines and how they work. Lack of consent to this will not preclude participation in the study. Where consent is given, any residual samples will be archived at -70 °C or below at PHE Colindale. Residual samples from participants who do not give such consent will be destroyed.

#### 8.5 LOSS TO FOLLOW-UP

All data for any participants withdrawn after receiving the study vaccination will be included in the data analyses, unless specific instruction for their destruction is received from the participant or their parent/guardian. Withdrawn participants will not be replaced (allowance for modest attrition is built into the sample size calculation).

#### 8.6 TRIAL CLOSURE

The study will be considered complete following enrolment of the last patient and completion of the study procedures in that patient. Upon review by the TSC, recruitment may be extended if target recruitment is achieved prior to end of the vaccination period for influenza and additional funding is available.

The study will be placed on hold and, upon review of study data and discussion with the IDMC, may be terminated early if any of the following occur:

- One patient suffers an allergic reaction or asthma episode that warrants admission to the ICU and use of mechanical ventilation
- Death of a participant during the study period, from any cause
- Two similar SUSARs (Suspected Unexpected Serious Adverse Reactions) or the repetition of one SUSAR

A teleconference will be scheduled within 72 hours if any of the aforementioned situations occur. This conference will be attended by the members of the IDMC and the TSC. At this teleconference the clinical relevance of the findings will be determined and recommendations may be made by the IDMC which may include:

- requesting further information
- modifying the protocol
- stopping enrolment
- institute more frequent monitoring guidelines

## 9. STATISTICS AND DATA ANALYSIS

### 9.1 DEFINITIONS

For the purpose of analyses, severity will be defined as follows:

- **Age 2-4 years (preschool wheezers, PSW):**
  - Step 3/4 BTS management:  $\geq 400$ mcg beclomethasone dipropionate /day or 200mcg/FP, AND LRTA (either continuous or intermittent or previous failed trial)

OR

  - $\geq 2$  exacerbations in the past year requiring oral steroids or observation in-hospital beyond 4 hours duration
- **Age 5+ years:**
  - Requiring Step 4+ management according to BTS Guidelines

A 'significant exacerbation' in asthma is defined as:

- i. At least 3 day course of oral steroids following an unscheduled contact with a healthcare professional; OR
- ii. Unscheduled visit to an Emergency department or admission to hospital for treatment of asthma symptoms, requiring systemic corticosteroids

### 9.2 SAMPLE SIZE ESTIMATION

Sample size is based on the primary objective of comparing the proportion of participants who experience a significant change in asthma control, as measured by a change in at least 3 points *and* from  $\geq 20$  on the (C-)ACT (good control) to  $< 20$  (sub-optimal control) in each group (BTS  $\leq 3$  vs BTS 4/5), or vice versa. In the SNIFFLE-2 study, such a change (one way or the other) was seen in about 20% of children (10% worse, 10% better).

A sample of 400 children in each group will provide sufficient power (5% significance level, 80% power) to detect an improvement in 10% vs deterioration in 17.5%, allowing for 10% attrition. In SNIFFLE-2, follow-up at four weeks was 89%. If the proportion of participants with a change in ACT score is less than this, with only 5% improving and 10% getting worse, a sample size of about 420 would provide a similar level of power. This would represent a conservative assumption in the proportions changing. For comparing the average change pre to post vaccination in ACT score between the severe and non-severe groups, the standard deviation of change from SNIFFLE-2 was used (about 3 units). With a sample size of 400 in each group the detectable difference is 0.6 units between the groups (80% power, 5% significance).

Assuming that about 1% of participants experience a significant deterioration in asthma control (as defined in 3.1.2 above), then the 95% CI for a significant deterioration will be from 0.027% to 2.54%. If 0/400 are observed the upper 95% CI is 0.92%.

---

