## 3. STUDY DESIGN

Type of Study:	Multicentre, observational study of the safety of LAIV in children with asthma or recurrent wheezing
Number of Subjects:	840 children: 420 on BTS/SIGN STEP 4+ treatment (the remainder on lesser levels of treatment) attending Paediatric Outpatients for routine clinic visits from September-January 2017 (see power calculation below)
Expected Duration:	Recruitment to commence 1 st September 2016 Clinical interventions to commence from mid-September 2016 for 5 months.

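### For 5% improving against 10% worsening, about 420 children per group gives roughly 71% to 76% power, not about 80%

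*Combined protocol and SAP*

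**What the plan says.** Section 9.2 works with two severity groups. Its main scenario puts 400 in each group, for 80% power at the 5% level, and the stated aim is "to detect an improvement in 10% vs deterioration in 17.5%, allowing for 10% attrition". It supports the attrition figure from the earlier study: "In SNIFFLE-2, follow-up at four weeks was 89"%. For a scenario in which fewer children change, it says that "with only 5% improving and 10% getting worse, a sample size of about 420 would provide a similar level of power", and comments: "This would represent a conservative assumption in the proportions changing".

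Section 3 adopts the larger figure as the target: "840 children: 420 on BTS/SIGN STEP 4+ treatment (the remainder on lesser levels of treatment"). Section 8.5 says that an "allowance for modest attrition is built into the sample size calculation". Section 9.3 names McNemar's test for the primary outcome. Section 9.2 itself names no test for the two proportions and does not say whether the 5% level is one- or two-sided.

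**The concern.** The second scenario has a smaller net effect (5 points rather than 7.5) and a smaller discordant proportion (15% rather than 27.5%). For a McNemar test the smaller difference raises the required sample and the smaller discordant proportion lowers it. Here the first effect dominates, so a 5% increase from 400 to 420 looks too small to hold power constant.

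The sentence is the plan's only check on power if fewer children change than expected, and it is presented as the cautious case. A reader would conclude that a true 10% worsening against 5% improving would be missed in a severity group about 20% of the time. If the real figure is higher, a non-significant result in the Step 4+ group, where the protocol says safety data are scarce, would be read as more reassuring than it is.

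**Working it through.** **Inputs.** From section 9.2: 5% significance, 80% power, 400 per group for 10% against 17.5%, about 420 for 5% against 10%, 10% attrition, 89% follow-up in the earlier study, and an SD of change of about 3. From section 9.3: McNemar's test. Two-sided testing is inferred in step 1.

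**Formulas.** Let pD be the sum of the two proportions changing and d their difference.

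- n = [z_α√pD + 0.8416√(pD − d²)]² / d²
- power = Φ{[d√n − z_α√pD] / √(pD − d²)}

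**Step 1: sidedness.** Section 9.2 says that "the detectable difference is 0.6 units between the groups (80% power, 5% significance") with 400 per group. Two-sided: (1.96 + 0.8416) × 3 × √(2/400) = 0.594. One-sided: (1.645 + 0.8416) × 3 × √(2/400) = 0.527. Only the two-sided value rounds to 0.6. The upper limit for 0/400 agrees: 1 − 0.025^(1/400) = 0.92% as stated, whereas a one-sided limit would be 0.75%.

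**Step 2: reproduce the 400 figure.** For 10% against 17.5%, pD = 0.275 and d = 0.075. Then n = 381.4 evaluable, and 381.4/0.9 = 424 enrolled. Power is 77.7% at 360 evaluable (400 less 10%; 78.3% by full enumeration of the uncorrected test), 79.6% at 378 and 81.9% at 400. The two-sided McNemar test therefore comes close to the plan's own statement.

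**Step 3: the 420 figure.** For 5% against 10%, pD = 0.15 and d = 0.05. Then n = 468.6 evaluable, and 468.6/0.9 = 521 enrolled. Power at 378 evaluable is Φ[(0.05 × 19.442 − 1.96 × 0.3873)/0.3841] = Φ(0.555) = 71.0%.

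| Evaluable per group | Power, 5% vs 10%, two-sided |
|---|---|
| 374 (89% follow-up) | 70.6% |
| 378 (10% attrition) | 71.0% |
| 420 (no attrition) | 75.5% |

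Enumerating the uncorrected test gives 71.7% at 378 and 76.3% at 420. Exact or continuity-corrected versions are lower, at about 67–68% and 72–73%.

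**Step 4: same convention for both scenarios.**

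| Convention | 400, 10% vs 17.5% | 420, 5% vs 10% | Gap (points, unrounded inputs) |
|---|---|---|---|
| Two-sided, 10% attrition | 77.7% | 71.0% | 6.6 |
| Two-sided, no attrition | 81.9% | 75.5% | 6.3 |
| One-sided, 10% attrition | 86.0% | 80.9% | 5.1 |
| One-sided, no attrition | 89.0% | 84.4% | 4.7 |

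The required samples stand in the ratio 468.6/381.4 = 1.23 (one-sided: 368.9/300.2 = 1.23). The plan's ratio is 420/400 = 1.05.

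**Step 5: other routes to 420.** A one-sided McNemar test needs 368.9/0.9 = 410 enrolled for the second scenario, but only 300.2/0.9 = 334 for the first. Treating the two percentages as independent samples gives 78.7% power at 420 and 74.3% at 378, but needs only 329.8/0.9 = 366 enrolled for the first. Neither route yields both 400 and 420.

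**The case against.** The wording is loose: the plan says about 420 and a similar level of power, and it mentions attrition only for the 400 figure. Read literally, the comparison is 77.7% (400 with attrition) against 75.5% (420 without), a gap of about 2 points. The miss in effect size is also small: with 5% improving, 80% power is reached at 10.3% worsening with 420 evaluable, or 10.7% with 378. Section 9.2 names no test, and section 9.3 does not say that McNemar's test is run within severity groups; it lists severity among the subgroup analyses. A pooled test on 756 evaluable children would have about 95% power. Finally, the study is observational, no decision rule depends on this scenario, and the sample size does not change.

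Some of this stands. The consequence is limited to the stated power and its interpretation, and the size of the shortfall depends on conventions the plan leaves unstated. The rest does not rescue the sentence. The 2-point gap requires dropping attrition one sentence after allowing for it, against section 8.5, and leaves both figures below 80%. Pooling conflicts with section 9.2, which frames the change and the sample size by group. No two-sided within-group McNemar calculation reaches 80% at 420.

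**Conclusion.** The concern holds. For 5% improving against 10% worsening, power within a severity group falls short of 80% by about 4 points if all 420 are evaluable and about 9 points after 10% attrition. A real difference of that size would be missed 24% to 29% of the time rather than 20%. This assumes a two-sided 5% McNemar test applied separately in each group. Two-sidedness is inferred from the other figures in section 9.2, and the within-group reading comes from that section's own framing. Whether 420 includes attrition is unresolved in the text, hence the range. The recruitment target is unaffected: 420 enrolled supports the 10% against 17.5% scenario at 79.6% power.

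**What to change.** Keep 840. In section 9.2, replace the sentence on 420 and drop the claim of similar power. Suggested text: *420 enrolled per severity group (378 evaluable after 10% attrition) gives about 80% power, using a two-sided 5% McNemar test within group, for 10% improving against 17.5% deteriorating, and about 71% for 5% against 10%; with 5% improving, 80% power is reached at about 10.7% deteriorating.* If the authors intended 420 to be evaluable children, they should say so and give about 76% instead.

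As a useful addition, though not needed to correct the arithmetic, report worse minus better with a 95% confidence interval in each severity group, so that a non-significant result is read against its precision. With 378 evaluable, the half-width is 1.96 × √((0.15 − 0.0025)/378) = 3.9 points at 5%/10% and 1.96 × √(0.20/378) = 4.5 points at 10%/10%.

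The cost is a less favourable stated power for one scenario and one interval per group. Participants, endpoint and procedures do not change.

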## 3.1 STUDY OUTCOMES MEASURES

### 3.1.1 PRIMARY STUDY OUTCOME

- Change in symptom/disease control assessment through validated questionnaire pre- and 4 weeks after LAIV in children with asthma / recurrent wheezing:
  - In children age 2-4 years inclusive: TRACK score (Appendix 1)
  - In children age 5-11 years: Children's Asthma Control Test (C-ACT) score (Appendix 2a)
  - In children age 12+ years: Asthma Control Test (ACT) score (Appendix 2b)

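### The 0.6-unit detectable difference in mean ACT change counts all 400 children per group, although those aged 2-4 are scored only on TRACK and no attrition is allowed for

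*Combined protocol and SAP*

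**What the plan says.** Section 9.2 contains two calculations. The first concerns a binary event, worded as a change of at least 3 points that crosses 20 "on the (C-)ACT (good control) to" sub-optimal control, or the reverse. Its planning rates come from SNIFFLE-2, where "such a change (one way or the other) was seen in about 20% of children (10% worse, 10% better". The sample of 400 per group is said to be enough "to detect an improvement in 10% vs deterioration in 17.5%, allowing for 10% attrition", and about 420 is given for a second scenario.

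The second calculation is introduced with "For comparing the average change pre to post vaccination in ACT score between the severe and non-severe groups". Its inputs are that "the standard deviation of change from SNIFFLE-2 was used (about 3 units") and "80% power, 5% significance". Its result is "With a sample size of 400 in each group the detectable difference is 0.6 units between the groups".

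Sections 1.3 and 3 set the target at 420 children per treatment-level group. The synopsis gives the age range as 2 to 18. Section 3.1.1 assigns the instruments by age: "In children age 2-4 years inclusive: TRACK score", C-ACT at 5-11 and ACT from 12. The schedule in section 6 and section 8.1.3 repeat this. Section 9.1 gives children aged 2-4 their own severity definition, and the analysis population stated after section 9.2 includes them. No section gives an age quota or an expected age mix.

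**The concern.** A mean change in ACT score can be computed only for children who have one. TRACK is a different scale: five items scored 0 to 20, total 0 to 100, with a minimum important difference of 10 points in section 9.3. A TRACK change cannot enter a mean whose SD is about 3 ACT units. Yet the mean-change sentence uses the full 400 per group, as if every child enrolled were scored on the (C-)ACT and followed to week 4. The 10% attrition allowance appears only in the binary sentence.

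The severe versus non-severe contrast addresses the evidence gap that motivates the study. Someone reading a null result on mean ACT change would take 0.6 units as the sensitivity of that comparison, when the ACT-scored children may support only something coarser. Children aged 2-4 are also a named subgroup in section 9.3, with no stated precision.

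**Working it through.** **Inputs from section 9.2:** SD of change about 3; significance 5% (sidedness not stated, taken as two-sided); power 80%; 400 per group; 10% attrition (from the binary sentence). **Input from sections 1.3 and 3:** target of 420 per group. **Assumption:** the share aged 2-4, called *f*, is not in the documents. It is varied from 0 to 40% and taken as equal in the two groups.

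**Step 1: reproduce the plan's figure.** Detectable difference = (1.96 + 0.8416) × SD × √(2/n). With SD 3 and n = 400: 2.8016 × 3 × √(2/400) = 0.594, which rounds to 0.6. In reverse, 0.6 units needs 393 change scores per group, and 400 gives 80.7% power. The stated figure is therefore reproduced with all 400 children contributing.

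**Step 2: attrition alone.** If 400 are enrolled, 360 remain and the difference is 0.63. If 420 are enrolled, 378 remain and it is 0.61. At the 89% follow-up seen in SNIFFLE-2, 420 gives 374, again 0.61.

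**Step 3: attrition and preschool share.** Evaluable n = 420 × 0.9 × (1 − *f*). Power for 0.6 units = Φ(0.6 / (3√(2/n)) − 1.96).

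| Preschool share *f* | (C-)ACT scores per group | Detectable difference | Power for 0.6 units |
|---|---|---|---|
| 0% | 378 | 0.61 | 79% |
| 10% | 340 | 0.64 | 74% |
| 20% | 302 | 0.68 | 69% |
| 30% | 265 | 0.73 | 63% |
| 40% | 227 | 0.79 | 57% |

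**Step 4: when does the printed figure change?** The difference reaches 0.65 at n = 2 × (3 × 2.8016 / 0.65)² ≈ 334. From 378 evaluable children, that is *f* = 1 − 334/378 ≈ 11-12%. Below about 11% preschool, the result still rounds to 0.6.

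**Step 5: unequal shares.** Children aged 2-4 who enter through the exacerbation criterion in section 4.2.1 meet the severity definition in section 9.1 automatically, so the severe group could hold more of them. As an illustration only, 40% preschool in the severe group and 10% in the other (227 and 340 scores) gives 2.8016 × 3 × √(1/227 + 1/340) = 0.72.

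**Step 6: the binary outcome.** Section 9.3 counts a TRACK change of at least 10 points ending below 80 as an event alongside the ACT event, and applies McNemar's test to TRACK or ACT. Children aged 2-4 therefore stay in that denominator. Section 9.2, however, words the event and its 10%/10% rates on the (C-)ACT only, so the planning tacitly gives TRACK the same rates. That need not hold: in Appendix 1, two of the five TRACK items look back 3 and 12 months, whereas the ACT items in Appendix 2b ask about the past 4 weeks.

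**The case against.** The strongest reply is that nothing is miscalculated. The sentence is conditional on 400 per group, the SD is only approximate, and the result has one decimal. Any n of about 335 or more rounds to 0.6, so the figure does not require 400 school-age children to complete week 4. This stands: the question is which n applies, and whether the printed figure moves depends on a preschool share that the documents do not give.

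The figure is also supplementary. The sample size was set by the binary comparison, and section 9.3 names no between-group test of mean ACT change. Even 0.79 units is well below the minimum important difference of about 2 points in children and 3 in adults cited in section 9.3. This stands too, and it limits the consequence.

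A reader might infer something stronger: that the primary analysis loses its preschool children, and with them its stated power. The documents do not support that, because section 9.3 supplies a TRACK event. What remains there is a mismatch of wording between 9.2 and 9.3 and an unstated rate.

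The reply does not remove the core point. The sentence names the ACT score, the groups it counts include children who will not have one, and it allows for neither them nor dropout.

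**Conclusion.** The concern holds for the mean-change sentence. Its 0.6 units rests on a number of ACT scores that the design does not supply unless preschool children are few. At 420 per group with 10% attrition, the realistic figure runs from 0.61 with no preschool children to 0.79 at 40% preschool, and power for 0.6 units falls from about 79% to about 57%. These values assume an SD of 3, a two-sided 5% test and equal preschool shares in the two groups. The share itself is an assumption throughout.

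It would be wrong to conclude that the 0.6 is an arithmetic error, that the trial is too small to detect clinically important mean differences on the ACT, or that the binary primary analysis is short of the children aged 2-4. For the binary outcome, the finding is limited to the missing TRACK planning rate.

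**What to change.** In section 9.2:

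- Restate the detectable difference for children aged 5 and over with a week-4 (C-)ACT score, giving the assumed preschool share and attrition. If the share is uncertain, a short range such as the table above will do.
- Limit the comparison of mean change to (C-)ACT-scored children, and report TRACK mean change separately.
- Define the binary planning event as the ACT-or-TRACK event of section 9.3, and state the event rate assumed for TRACK.

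These are changes of text only. No extra patients are needed, and the one cost is a slightly less favourable stated figure.
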